Basal-state responses will be compared in samples from the 2nd muscle biopsy, whereas responses induced by the experimental manipulations will be evaluated in samples from the 3rd and 4th muscle biopsies. Muscle samples will be analyzed for mRNA and protein expression of MHC-I, MHCII-a, and MHC-IIx. We will quantify muscle miRNA-208b and miRNA-499 because of their role in regulating the overall muscle fiber phenotype programming. We will determine relevant molecular mechanisms regulating signaling for protein synthesis in muscle, importantly the eIF4G·eIF4E and 4E-BP1·eIF4E complexes, given that our preliminary evidence shows dysregulation of the eIF4G·eIF4E complex formation in muscle of humans with obesity. We will evaluate canonical signaling regulating protein synthesis in muscle by evaluating phosphorylation (and total protein) of relative proteins, such as AKT, mTOR, 4E-BP1, S6K1, S6K1. GAPDH will be employed as loading control and to normalize western blot signal intensities. We will evaluate well-established molecular markers relevant to protein breakdown to complement our main findings on muscle protein breakdown measured *in vivo*. We propose to focus on muscle specific ubiquitin ligases, RING finger-1 (MuRF-1) and muscle atrophy F-box (MAFbx), which are important in the regulation of the ubiquitin-proteasome system, and which appear to increase in obesity (95), and are also regulated by acute aerobic exercise (96-101). Additional potential measurements include evaluation of their transcriptional regulation by measuring FOXO transcription factors, which are in turn regulated by Akt (102, 103), and whose mRNA levels also appear to increase following aerobic exercise (97, 99, 100, 104). Other candidate markers include those related to autophagy and could be evaluated by blotting for ULK1 phosphorylation, processed LC3, and p62 expression who appear to be modulated by obesity, exercise, and/or insulin (104-107). [name], a Co-Investigator in this project, has several decades of experience on

Date: February 23, 2024

Protocol V11

muscle protein metabolism and an established research program focusing on the intracellular mechanisms that regulate protein metabolism (108, 109). He will direct all the aspects of the proposed research related to molecular mechanisms explaining the observed protein turnover responses in vivo.

Analyses of Samples and Calculations

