Stable isotope enrichment and MHC quantification. Muscle for the determination of mixed-muscle protein turnover will be processed following procedures we have previously described (8, 87, 89, 91). Mitochondria will be isolated from muscle using procedures we have also previously described (17, 110, 111). Mixed-muscle protein, mixed-mitochondrial protein, and blood samples will be analyzed for determination of amino acid enrichment (i.e., d₉-leucine, ¹³C₆- and ¹⁵N-phenylalanine) using LC-MS/MS (87). Enrichment of the MHC isoforms with d₉-leucine will be based on the determination of the incorporation of d₉-leucine on selected peptides of the MHC isoforms, following procedures similar to those we have previously described (112). Peptides studied will correspond to MHC-I [NTQAILK(+2), SALAHALQSSR (+3)], MHC-IIa [SLGTELFK(+2), IEDEQALGIQLQK(+2)], and MHC-IIx [SVNDLTSQR(+2), DSLVLIQWNIR(+2)]. MS1 data (when compared to MS2) data offer the advantage of determining enrichment by using peptides that have more than one amino acid in their sequence that can be labeled. This is because for a peptide with, for example, 2 possible positions for d₉-leucine, each one of those 2 amino acids has equal probability, that is 50%, to be labeled with d₉-leucine. Therefore, by targeting unlabeled and single-labeled peptides, the resulting true enrichment of that peptide with labeled amino acids will be (labeled AUC+2)/unlabeled AUC. We have determined that having peptides that can be labeled in 2 amino acid (i.e., leucine) residues enhances the signal of the labeled peptide, and improves the reproducibility of the measured enrichment. MHC isoform enrichment will be determined by calculating an average enrichment from the enrichments measured for its corresponding targeted peptides. Standard proteomics analyses will be performed for the determination of MHC isoforms abundance, following procedures similar to those we have used previously (17, 113). Determination of the abundance of MHC isoforms in muscle samples, which will be used to determine the fractional change in the MHC isoform concentrations over time, will be performed by spiking the muscle samples using stable isotope-labeled full-length proteins corresponding to the MHC isoforms, and which will be commercially obtained (OriGene Technologies, Inc., Rockville, MD). Characterization of the MHC content of isolated muscle fibers will be done using gel electrophoresis, and as described here (119). The proteome of individual muscle fibers will be evaluated using laboratory procedures described here (120), while their transcriptome and metabolome will be evaluated using experimental techniques currently under development in our laboratory.

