
Calculations. Fractional synthetic rate of mixed-muscle and mixed-mitochondrial proteins will be determined using the precursor-product method based on the phenylalanine amino acid enrichments measured in the blood amino acid and muscle protein pools, following procedures we have recently described (8, 9, 87). Fractional breakdown rate of mixed-muscle protein will be determined directly in muscle (i.e., *not by using the arterio-venous technique*) following procedures previously described (84-86). We have previously validated a method to determine application of the d₁₀-leucine tracer to measure fractional synthetic rate of protein in muscle (87). Fractional synthetic rate of individual MHC isoforms will be calculated from d₉-leucine enrichments measured in the blood and the muscle MHC isoforms (i.e., MHC-I, MHC-IIa, MHC-IIx). We have previously developed (112), and successfully applied (9) a methodology to measure the fractional synthesis rate of an individual protein in skeletal muscle, and we will use similar procedures with respect to the fractional synthesis rates of the MHC isoforms. Fractional breakdown rate of the individuals MHC isoforms will be calculated from the measurement of the fractional synthesis rate of each MHC isoform in combination with the fractional change in that MHC isoform's concentration over a given time period, and as previously described (114, 115).

Immunoprecipitation and immunoblotting. We will follow procedures similar to those we and [name] have used in the past (7, 8, 116-118). With respect to the 4E-BP1·eIF4E and eIF4G·eIF4E complexes (which are key measurements in this proposal), these will be quantified after eIF4E is immunoprecipitated (IP) from aliquots of supernatants using an anti-eIF4E monoclonal antibody (generated in [name] laboratory). Antibodies not generated in [name] laboratory will be commercially obtained and authenticated in [name] laboratory. We will also measure in the same muscle samples MOTS-c (mitochondrial open reading frame of the twelve S rRNA type-c). MOTS-c will be measured in muscle samples as well as plasma samples.

Date: February 23, 2024

Protocol V11

MOTS-c is a novel mitochondrial peptide in muscle, and which is also released into the circulation in association with physical activity/exercise. Recent evidence shows that it regulates metabolic processes in muscle that can be linked to protein synthesis.

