We will perform the following measurements in our effort to explain differences in protein synthesis in muscle and understand regulation of the MHC genes in humans with obesity versus the lean controls: plasma and muscle insulin growth factor 1 (IGF-1) and associated hormones (i.e., growth hormone) and binding proteins that determine the IGF-1 function; plasma cytokines, such as TNF α , IL-6, IL-8, IL-10 (cytokine measurements will be performed by [name] laboratory at ASU); chromatin-associated modification in isolated DNA from the muscle samples (DNA modification measurements will be performed by [name] laboratory at Mayo Clinic-Arizona). We will identify mechanisms involved in the responses we observe in vivo (i.e., differences in protein synthesis and MHC isoform expression between muscle from lean subjects and muscle from subjects with obesity) by performing in vitro, cell culture experiments, and where myoblasts isolated from the muscle biopsy samples are propagated to myotubes and associated changes in protein synthesis and MHC in response to changes in the expression of regulatory factors (i.e., IGF-1) can be modified in the absence of any other hormonal or metabolic differences.

Real-time quantitative PCR determination of gene expression. Expression of genes in skeletal muscle will be determined following procedures we have previously described (7, 8). Briefly, isolated mRNA will be purified using the RNeasy MinElute Cleanup Kit and be used to perform cDNA synthesis using the ABI High Capacity cDNA Reverse Transcription kit. Real time PCR will be performed on an Applied Biosystems 7900HT Fast Real-Time PCR System using pre-designed TaqMan® gene expression assays (probe/primer sets from ThermoFisher Scientific), and by following the manufacturer's protocols. The mRNA levels will be normalized to GAPDH, and relative differences in the mRNA levels will be analyzed by the $2^{-\Delta\Delta CT}$ method. miRNA-208b and miRNA-499 in muscle will be quantified following procedures we have previously described (7), and normalized to RNU-6B. Blood chemistry parameters will be quantified using commercially available assays and kits.

Statistical Design and Power

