Our main end-points in the proposed studies are the synthesis rates of mixed-muscle protein, mixed-mitochondrial protein, as well as MHC isoforms, particularly MHC-I, whose synthesis rate we found to be lower in subjects with obesity, in our preliminary studies. These preliminary data also show that MHC-I synthesis rate does not increase in response to our experimental manipulation (i.e., exercise stimulus alone) despite an increase in MHC-I mRNA. Therefore, other main end-points are the expression of mRNA of MHC isoforms as well as the formation of the active eIF4F complex, which has key role in translation initiation in skeletal muscle, and which we found in our preliminary studies to be lower in muscle from humans with obesity. Statistical significance will be calculated using 2-way repeated measures ANOVA.

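### GAPDH is the only stated reference for MHC isoform mRNA, a main end-point, and no check is planned that it is stable between lean and obese muscle or across biopsies

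*Combined protocol and SAP*

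**What the plan says.** Under Real-time quantitative PCR determination of gene expression, the protocol states that "The mRNA levels will be normalized to GAPDH" and that "relative differences in the mRNA levels will be analyzed by the" 2^-ΔΔCT method. The two microRNAs are treated separately and are "normalized to RNU-6B". No further reference gene for mRNA and no stability assessment is described.

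Under Statistical Design and Power, after the synthesis rates, "other main end-points are the expression of mRNA of MHC isoforms as well as the formation of the active eIF4F complex". The same section makes the post-exercise rise in MHC-I mRNA the main outcome of the exercise-alone trial and sizes it at 9 per group for a 0.94 SD change. It also quotes a 1.26 SD basal group difference in MHC-IIx mRNA.

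Under Variables Determined in Muscle and Blood Samples, "GAPDH will be employed as loading control and to normalize western blot signal intensities". The eIF4E complexes are described separately under Immunoprecipitation and immunoblotting: "these will be quantified after eIF4E is immunoprecipitated (IP) from aliquots of supernatants". No normaliser for those precipitates is given there.

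**The concern.** A reference gene is useful only if it does not move with the factors under study. GAPDH encodes an enzyme of glycolysis; this is general biochemistry and is not stated in the protocol. The Significance section argues that fibre types differ in their glucose-handling proteins (transporters, hexokinase II, glycogen synthase) and that obese muscle has fewer Type I fibres. On the protocol's own premise, then, the constancy of a glucose-pathway gene between these groups needs to be shown. Lean versus obese is not a randomised contrast, and samples are also compared across exercise and amino acid infusion.

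The inference most exposed is translational resistance: MHC-I mRNA rises after exercise while MHC-I synthesis does not. Synthesis comes from tracer enrichment and does not involve GAPDH. A fall in GAPDH after exercise would therefore raise apparent MHC-I mRNA alone and could imitate that dissociation.

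**Working it through.** **1. The plan's own figure.** For the exercise-alone trial the inputs are n = 9 per group, d = 0.94 SD, α = 0.05 and 80% power (Statistical Design and Power). The two-sided paired normal approximation gives Φ(0.94 × √9 − 1.96) = Φ(0.86) = 80.5%, which reproduces the stated 80%. The exact two-sided paired t-test gives 69.6%. That gap is a separate matter; the exact figure is used as the base in step 4.

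**2. How a reference shift enters.** ΔCT = CT(MHC) − CT(GAPDH), and the result is 2^-ΔΔCT. If GAPDH expression differs by a factor g between two conditions, then

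apparent fold = true fold ÷ g.

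The documents give no GAPDH data, so g is assumed:

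| GAPDH fold (assumed) | MHC-I mRNA, no true change | MHC-IIx mRNA, assumed true rise 1.3-fold |
|---|---|---|
| 1.2 | 1/1.2 = 0.83 (17% lower) | 1.3/1.2 = 1.08 |
| 1.3 | 1/1.3 = 0.77 (23% lower) | 1.3/1.3 = 1.00 |
| 1.5 | 1/1.5 = 0.67 (33% lower) | 1.3/1.5 = 0.87 |

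**3. The same on the Ct scale.** A GAPDH shift of 0.25, 0.5 or 1.0 Ct gives a false change of 2^0.25 = 1.19-, 2^0.5 = 1.41- or 2^1 = 2.00-fold. The sign depends on the direction of the shift.

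**4. Effect on the tests.** Let k be the shift in SD units of the normalised measure (assumed, because no Ct SD is given). With no true MHC change, the rejection rate of a two-sided 5% test follows a noncentral t. The noncentrality is k√9 on 8 df for the paired n = 9 test, and k√(17/2) on 32 df for 17 versus 17.

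| k (assumed) | Paired, n = 9 | 17 versus 17 |
|---|---|---|
| 0.1 | 5.8% | 5.9% |
| 0.25 | 10.2% | 10.9% |
| 0.5 | 26.3% | 29.3% |

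A 0.5 SD shift against a true effect leaves 0.94 − 0.5 = 0.44 SD, and exact power falls from 69.6% to 21.4% (n = 9). For basal MHC-IIx it leaves 1.26 − 0.5 = 0.76 SD, and power falls from 94.5% to 57.5% (17 per group). Noncentrality grows with √n, so a larger sample makes a reference artefact more likely to reach significance.

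**5. Which end-points are exposed.**
- MHC isoform mRNA: exposed, since GAPDH is its only stated reference.
- Synthesis rates: not exposed. "Fractional synthetic rate of individual MHC isoforms will be calculated from" tracer enrichments in blood and in the isoforms, and the mixed-muscle and mitochondrial rates also come from enrichments.
- MHC protein abundance: not exposed. It "will be performed by spiking the muscle samples using stable isotope-labeled full-length proteins".
- eIF4F formation: undetermined, because the normaliser for the precipitate is not stated.

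**The case against.** Several counter-arguments have force.

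- **The bias is conjectural.** Nothing in the documents says that GAPDH changes with obesity, fibre type, exercise or amino acids. The figures above show sensitivity, not likelihood. This stands, and it limits the point to a conditional risk.
- **The PCR paragraph is a brief summary that cites earlier procedures.** Reference validation may be described there. That is possible, but even so, validation in other samples would not replace a check in these groups and at these biopsies.
- **The plan has readouts that do not use GAPDH.** miRNA-208b, hosted in the MHC-I gene, has its own reference; MHC protein uses spiked standards; basal fibres are typed and profiled. These partly corroborate MHC-I expression. None is designated as a check on the reference gene, and the fibre work covers the basal state only.

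Three stronger readings are tempting and are not supported:

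- A reader might infer that the main end-points as a whole are compromised. The synthesis rates, named first, and MHC protein abundance do not depend on GAPDH.
- A reader might infer that GAPDH could manufacture the whole Aim 1 mRNA pattern. Aim 1 expects MHC-I lower and MHC-IIx higher in obesity. One shared denominator moves both the same way, so it can distort either result but cannot create the opposite pair. Higher GAPDH would work against the MHC-IIx hypothesis.
- A reader might infer that the eIF4E precipitates will be normalised to GAPDH, so that differences in eIF4E recovery would pass for differences in complex formation. A lysate loading control would indeed not correct for recovery, but no sentence applies GAPDH to the precipitates. The blot sentence follows a list of signalling proteins, and the complexes are described elsewhere by reference to cited procedures. This is a missing detail, not a demonstrated error.

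**Conclusion.** The point holds for MHC isoform mRNA only. It rests on a single stated reference gene with no stated stability check, in a comparison where the protocol's own premise gives reason to check. A shift would pass undiminished into a main end-point and into the main outcome of the exercise-alone trial. Under an assumed 1.2- to 1.5-fold GAPDH difference, MHC-I mRNA would appear 17% to 33% lower. Under an assumed 0.5 SD shift, the 5% error rate would become 26.3% (paired, n = 9) or 29.3% (17 versus 17). Whether any shift occurs, and in which direction, cannot be settled from the documents. The change is worth making because it is cheap and guards a main end-point, not because an error has been shown. For eIF4F, only a clarification is warranted.

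**What to change.** In Real-time quantitative PCR determination of gene expression:

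- Normalise MHC mRNA to the geometric mean of two or three non-glycolytic reference genes, run on the existing cDNA at equal RNA input. If one of three references shifts by 0.5 Ct, the artefact is 2^(0.5/3) = 1.12-fold, against 1.41-fold when that gene is the only reference.
- Choose the genes by a stability measure or equivalence margin fixed in advance. A non-significant Ct difference at 9 or 17 per group would not establish stability. As an illustration, holding the combined reference within 0.25 Ct caps the artefact at 1.19-fold.
- Report Ct for GAPDH and for each reference gene by group and biopsy. The GAPDH values will exist already.
- Keep the GAPDH-normalised result as a sensitivity analysis, for comparison with the preliminary data behind the 0.94 SD and 1.26 SD effect sizes.

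As a clarification only, in Variables Determined in Muscle and Blood Samples and in Immunoprecipitation and immunoblotting, state that eIF4G and 4E-BP1 in the precipitate are expressed per eIF4E recovered in the same precipitate.

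The cost is a few extra assays and some bench time, with no added procedure for subjects. The primary mRNA result becomes less directly comparable with the preliminary data, which the sensitivity analysis addresses.

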
Date: February 23, 2024

Protocol V11

contributes to lower synthesis and expression of MHC-I. On the other hand, failure to increase synthesis rate of MHC-I under these conditions, will suggest a defect that is specific to the MHC-I translation. Our studies will, therefore, pinpoint specific biological defects that sustain unfavorable muscle fiber phenotype in humans with obesity, and which is key in any effort to address metabolic abnormalities (i.e., impaired muscle glucose uptake) originating from an unfavorable muscle fiber phenotype in these humans.

Specific Aims

Aim 1. To determine the turnover rate of MHC isoforms and overall muscle protein in skeletal muscle of subjects with obesity and lean controls in the basal state. We hypothesize lower synthesis rate of MHC-I (due at least in part to lower MHC-I mRNA) along with lower overall muscle protein synthesis in skeletal muscle of humans with obesity, and concomitant with lower formation of the eukaryotic initiation factor 4F (eIF4F) in muscle (key protein-complex signaling overall translation/synthesis). We hypothesize that muscle MHC-IIx synthesis is not reduced in obesity, and despite lower eIF4F complex formation in muscle, because the presence of higher MHC-IIx mRNA expression in muscle of humans with obesity.

Aim 2. To determine stimulation of the turnover rate of MHC isoforms in skeletal muscle of subjects with obesity and lean controls by plasma amino acids and with and without prior exercise. We hypothesize that increasing the plasma amino acid concentrations alone increases the basal rate of synthesis across all MHC isoforms in both lean and obese subjects, revealing a response largely dependent upon their respective mRNA expressions. This is because plasma amino acids enhance the overall protein translation in muscle (i.e., increase muscle eIF4F complex formation). We hypothesize that acute aerobic exercise alone does not increase the basal-state MHC-I synthesis rate in either lean or obese subjects, and despite greater increase in MHC-I mRNA expression in muscle of subjects with obesity. Thus, we also hypothesize that coupling the plasma amino acid stimulus to the exercise stimulus will increase the synthesis rate of the MHC-I in the subjects with obesity, revealing that impaired overall muscle protein translation is also responsible (and in addition to lower basal-state MHC-I mRNA, Aim#1) for lower MHC-I expression in muscle of humans with obesity.

Approach

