concentrations coupled to the exercise stimulus, and another 17 will serve as controls, for a total 34 lean subjects participating in the study. Main outcome in the exercise-alone studies is the increase in MHC-I mRNA expression after aerobic exercise, and which we show to increase only in the subjects with obesity. In our preliminary studies we detected a difference of 0.94 SD for MHC-I mRNA expression between before and after exercise in subjects with obesity. A sample of 9 subjects per group will have sufficient power (80%) to detect 0.94 SD difference ($\alpha = 0.05$) in MHC-I mRNA expression. Therefore, we will study 9 lean subjects and 9 subjects with obesity in the groups that will undergo exercise-alone trial. Sample size estimates and power were calculated using paired t-tests with an overall $\alpha = 0.05$ and $\alpha = 0.0125$ for Bonferroni-adjusted multiple comparisons. We propose to enroll 2 more subjects/group for the amino acid infusion and exercise+amino acid infusion studies (to the overall 34 subjects per group indicated above for those studies), to account for unsuccessful experiments and/or increase the statistical power in pair-wise comparisons with the lowest effect size, for a total of 36 lean subjects and 36 subjects with obesity for the studies related to the amino acid infusion and exercise+amino acid infusion. Therefore, we will enroll a total of 90 subjects.

Protection of Human Subjects

Risks to Human Subjects

Human Subjects Involvement, Characteristics, and Design

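### Aim 2 expects a greater MHC-I mRNA rise after exercise in obese than in lean subjects, but the exercise-alone groups are sized only on a within-obese before/after change, and no power is given for the lean-versus-obese difference

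*Combined protocol and SAP*

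**What the plan says.** Specific Aims, Aim 2, hypothesises that exercise alone does not raise MHC-I synthesis in either group, "despite greater increase in MHC-I mRNA expression in muscle of subjects with obesity".

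Statistical Design and Power gives the main outcome of the exercise-alone studies as the "increase in MHC-I mRNA expression after aerobic exercise, and which we show to increase only in the subjects with obesity". For the effect size it says "we detected a difference of 0.94 SD for MHC-I mRNA expression between before and after exercise in subjects with obesity". It then states that "A sample of 9 subjects per group will have sufficient power (80%) to detect 0.94 SD difference", at alpha 0.05, and that "we will study 9 lean subjects and 9 subjects with obesity in the groups that will undergo exercise-alone trial". Sample sizes and power are said to come from paired t-tests, with an overall alpha of 0.05 and 0.0125 for Bonferroni-adjusted comparisons. Sidedness is not given, nor is it said whether the SD is that of the change or of the raw values.

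For the analysis, the same section says "Statistical significance will be calculated using 2-way repeated measures ANOVA", without naming the two factors or the term that answers each hypothesis. No power is stated anywhere for a lean-versus-obese difference in mRNA change.

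**The concern.** A greater increase in one group than in the other is a difference between two changes. In a two-group, two-time-point repeated measures ANOVA it is the group-by-time interaction. The sizing uses only the obese group's own before/after change, so it says nothing about how well 9 lean and 9 obese subjects can separate the two responses. Because the plan expects no mRNA rise in lean subjects, their main use for this variable is as the comparator, and that comparison has no stated power.

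At stake is the comparative part of Aim 2. If the exercise-alone groups give an imprecise difference in change, a true excess response in obesity could easily be missed, and the power statement would not have warned the reader.

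**Working it through.** **Inputs.** From Statistical Design and Power: effect 0.94 SD, n = 9 per group, alpha 0.05 (0.0125 for Bonferroni), paired t-test. Assumptions: two-sided tests, equal SDs in both groups and, unless varied below, zero change in lean subjects and 0.94 in SDs of the change.

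**1. The plan's own figure (paired, within obese).**
- Noncentrality: 0.94 × √9 = 2.82.
- Normal approximation: Φ(2.82 − 1.96) = Φ(0.86) = 80.5%. This reproduces the printed 80%; the required n is (2.80/0.94)² = 8.9, rounded up to 9.
- Exact paired t, 8 df, critical value 2.306: 69.6%. Reaching 80% needs 11 subjects (80.2%).
- Exact paired t at alpha 0.0125: 41.5%.

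**2. The lean-versus-obese difference in change.** This equals a two-sample t-test on the individual changes.
- Noncentrality: 0.94 × √(9/2) = 1.994, with 16 df and critical value 2.120.
- Power, exact t: 46.6% (46.5% by simulation). At alpha 0.0125: 24.4%.
- Normal approximation: Φ(1.994 − 1.96) = 51.4%.
- 80% power needs 19 per group by exact t, or 18 by normal approximation.
- If lean subjects also rise by 0.25 SD, the difference is 0.69 SD and power is 28.0%.

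**3. Sensitivity to the SD scale.** If 0.94 is in raw-value SDs and the before/after correlation is ρ, the effect in change SDs is 0.94/√(2(1 − ρ)).

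| ρ | effect, change SDs | paired t, n = 9 | group-by-time, 9 v 9 |
|---|---|---|---|
| 0 | 0.66 | 42% | 26% |
| 0.5 | 0.94 | 70% | 47% |
| 0.61 | 1.07 | 80% | 57% |
| 0.7 | 1.21 | 89% | 68% |
| 0.8 | 1.49 | 97% | 84% |

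The correlation at which the exact paired t-test gives the printed 80% is about 0.61. There the group-by-time power is about 57%.

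**4. What pooling the exercisers would give.** EX has 9 per BMI group. EX+AA has 17, or 18 if the 36 enrolled per BMI group split evenly. The total is 26 or 27 per BMI group.
- Trial main effect only: standard error √(2/26) = 0.277, noncentrality 0.94/0.277 = 3.39, power 91% (78% at 0.0125). With 27: 92% (80%).
- Group-by-trial fitted, trials weighted equally: standard error ½√(2/9 + 2/17) = 0.291, noncentrality 3.22, power 88% (73% at 0.0125). With 18 in EX+AA: 89% (74%).
- The group-by-trial check itself: standard error √(2/9 + 2/17) = 0.583, noncentrality 0.94/0.583 = 1.61, so about 35% power even if amino acids shift the group difference by a full 0.94 SD.

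**The case against.** The strongest reply is that these groups were not set up to compare lean with obese mRNA responses. The Experiments section gives their purpose as testing that exercise alone does not stimulate MHC-I synthesis although mRNA rises. The power section names the increase after exercise as the main outcome. Both are within-group, and a paired test fits them. In Aim 2 the larger obese response stands in a subordinate clause, and the remark about a rise only in obesity reports preliminary data. The translational-resistance argument in the Significance section rests on subjects with obesity alone. All of this stands. It limits the point to a comparison that the plan expects but does not power; it does not make the paired sizing wrong for its own outcome.

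A reader might infer that power falls from a claimed 80% to 47%. The documents do not support that: the 80% was never stated for group-by-time, and the two figures also mix methods. Like for like, the pairs are 80.5% and 51% by normal approximation, or 70% and 47% by exact t. Nor is 47% a ceiling, since the SD scale is not stated and a high before/after correlation would raise it.

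A reader might also infer that the group difference will be read from two separate paired tests. With equal true rises of 0.94 SD, that would give a significant result in obese but not in lean subjects 0.696 × 0.304 = 21% of the time. The plan nowhere proposes this, and the ANOVA it names can supply the interaction.

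**Conclusion.** The point holds in limited form. Aim 2 carries a lean-versus-obese expectation for the mRNA response, the exercise-alone sizing does not address it, and the ANOVA term that would test it is not named. Power for that contrast at 9 per group is about 47% if 0.94 SD is on the change-score scale, lean change is zero, SDs are equal and alpha is 0.05 two-sided. Across raw-value correlations of 0 to 0.8 it runs from 26% to 84%; a non-zero lean rise lowers it.

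Separately, the printed within-group 80% is about 70% under the paired t-test that the plan names, unless the SD is a raw-value SD with a correlation near 0.61. The conclusion does not extend to saying that the stated main outcome is tested with the wrong method.

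**What to change.** In Statistical Design and Power:

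1. Say that the stated power covers only the within-group before/after change. Restate it as about 70% for the paired t-test at n = 9, or give the SD scale and correlation that yield 80%. Give the power for the lean-versus-obese difference in change as a range, with its assumptions.
2. Name the ANOVA factors, and name group-by-time as the term that tests a greater increase in obesity.
3. Keep the EX-only estimate of the group difference, with its confidence interval, as the answer for exercise alone. Add a supporting group-by-time analysis pooling EX and EX+AA at biopsies 2 and 3, with trial and group-by-trial terms. The section on variables determined in muscle and blood already plans the assays: "Muscle samples will be analyzed for mRNA and protein expression of MHC-I, MHCII-a, and MHC-IIx". At 0.94 change SDs its power is about 88–89% with group-by-trial fitted and equal trial weights, or 91–92% without that term (73–74% or 78–80% at alpha 0.0125).

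The cost is wording and one extra model, with no added subjects, biopsies or assays. The downside is that EX+AA subjects have had about 45 minutes of amino acids by biopsy 3. The pooled result therefore assumes that amino acids leave the lean-versus-obese difference in mRNA response unchanged. A trial main effect cannot test this, and the group-by-trial term tests it only weakly (about 35% power). The pooled result should be labelled as supporting evidence under that stated assumption.

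### Under a conventional two-sided paired t-test, 9 subjects per group give about 70% power for the exercise-alone main outcome, not the stated 80%; sidedness and the SD behind 0.94 are not stated

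*Combined protocol and SAP*

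**What the plan says.** All of the relevant text is in the Statistical Design and Power section of the combined protocol and SAP.

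- Outcome: "Main outcome in the exercise-alone studies is the increase in MHC-I mRNA expression after aerobic exercise". The preliminary work is said to show this increase only in subjects with obesity.
- Planning effect: "we detected a difference of 0.94 SD for MHC-I mRNA expression between before and after exercise in subjects with obesity".
- Sample size and power: "A sample of 9 subjects per group will have sufficient power (80%) to detect 0.94 SD difference", at alpha 0.05. The plan therefore studies 9 lean subjects and 9 with obesity.
- Method for the power figures: "Sample size estimates and power were calculated using paired t-tests". The same sentence gives an overall alpha of 0.05 and an alpha of 0.0125 for Bonferroni-adjusted comparisons, which it does not list.
- Planned analysis, earlier in the section: "Statistical significance will be calculated using 2-way repeated measures ANOVA".

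The documents do not say whether any test is one-sided. They also do not say whether 0.94 SD is in units of the SD of the paired differences or of the SD of single measurements.

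**The concern.** The plan gives a sample size, an effect, an alpha, a named test and a power. Put through the named test in its usual two-sided form, these do not agree: the power falls about 10 points short.

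This calculation is the only basis given for the size of the EX groups. The Experiments section uses the EX trial to test whether exercise alone fails to stimulate MHC-I synthesis even though MHC-I mRNA rises. That argument needs the mRNA rise to be shown. At 70% power, a true effect equal to the planning value would be missed about 30% of the time (100 − 69.6 = 30.4%), and the argument would then lack its mRNA half. A reader relying on the stated 80% would expect a miss 20% of the time.

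**Working it through.** **Inputs from the plan.** n = 9 in the group with obesity; standardised pre-post difference d = 0.94; alpha = 0.05; paired t-test. **Assumed where the plan is silent:** d is the mean difference divided by the SD of the paired differences, except in step 6.

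**Formula.** The paired t statistic follows a noncentral t distribution with df = n − 1 and noncentrality d·√n. For n = 9, df = 8 and the noncentrality is 0.94 × 3 = 2.82. Power is the probability of exceeding the critical value.

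**1. Recovering the plan's figure.** Two variants return 9 subjects.
- One-sided paired t-test, alpha 0.05: critical value 1.860, power 82.3%. With n = 8 the power is 77.2%, so 9 is the smallest n that reaches 80%.
- Two-sided normal approximation: n = ((1.960 + 0.842)/0.94)² = 8.88, rounded up to 9. Power = Φ(2.82 − 1.96) = Φ(0.86) = 80.5%.

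**2. The named test, two-sided.** The critical value of t with 8 df is 2.306. Power is **69.6%**. The normal approximation in step 1 overstates this by 80.5 − 69.6 = 10.9 points, because it uses 1.96 where the t-test with 8 df needs 2.306.

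**3. Sample size for two-sided 80%.** n = 10 gives 75.4% and n = 11 gives 80.2%, so **11** subjects are needed.

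**4. Detectable effect at n = 9.** Solving for 80% two-sided power gives d = 1.067, or **1.07 SD**.

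**5. Using the planned ANOVA.** Suppose the pre-post contrast in subjects with obesity takes its error term from both EX groups together. Then df = 2 × (9 − 1) = 16, the critical value is 2.120, and the noncentrality stays at 2.82 if the SD of change is the same in lean subjects and subjects with obesity. Power is 75.4%, still below 80%.

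**6. If 0.94 is in SDs of single values.** With equal SDs before and after and pre-post correlation r, the standardised paired difference is 0.94/√(2(1 − r)). Two-sided power at n = 9 and alpha 0.05 is then:

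| r | Standardised paired difference | Power |
|---|---|---|
| 0 | 0.66 | 42% |
| 0.3 | 0.79 | 55% |
| 0.5 | 0.94 | 70% |
| 0.6 | 1.05 | 79% |
| 0.7 | 1.21 | 89% |

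Power reaches 80% at r of about 0.61. The plan gives no correlation, so this range cannot be narrowed from the documents.

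**The case against.** The strongest reply is that the plan never says two-sided. The outcome is worded as an increase, and a one-sided paired t-test makes 9 exactly the smallest sufficient number. This stands as a possible account of how 9 was reached. It does not settle the matter: the one-sided test is not declared, and the only analysis the plan names is an ANOVA, whose F-test has no direction.

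A reader might infer that a one-sided alpha is the only way to reach 80%. That is wrong, since the two-sided normal approximation also returns 9 subjects and 80.5%. It is a common planning shortcut, but it is not the t-test that the plan names, and at 9 subjects it is too optimistic.

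A second fair point is that 69.6% depends on the SD. If 0.94 is in SDs of single values and the pre-post correlation is about 0.61 or higher, 9 subjects do reach 80% two-sided. This stands, and it makes the shortfall conditional.

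A third is that a single-group t-test with 8 df is not the analysis that will be run. This also stands in part: pooling the ANOVA error closes about half of the gap, but not all of it.

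Two stronger readings are tempting and not supported:
- That power is really 41%. The two-sided paired t-test at alpha 0.0125 does give 41.5%, but the stated 80% is tied to alpha 0.05, and the plan does not say that the Bonferroni level covers this outcome. It is a sensitivity figure and contradicts nothing in the plan.
- That the EX groups wrongly lack spare subjects. The plan gives the 2 extra per group to the other two trials, and 36 + 36 + 9 + 9 = 90 agrees with that. This is an open design choice, not an arithmetic error.

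**Conclusion.** The concern holds, conditionally. On the conventional reading of the plan's own method (two-sided paired t-test, alpha 0.05, 0.94 in SDs of the paired differences), 9 subjects give 69.6% power, about 10 points below the stated 80%. With pooled ANOVA error and equal variances the figure is about 75%. The 80% cannot be confirmed as written, because sidedness and the SD are both missing and the variants that recover it are either undeclared or not the named test.

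The documents do not support a flat statement that 9 subjects cannot give 80%: a declared one-sided test would, and so would a sufficiently high pre-post correlation if 0.94 is in single-value SDs.

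The severity is moderate. The calculation sets the size of the EX groups, but these are 18 of 90 subjects, and the section lists the MHC mRNA endpoints after the synthesis rates. The correction should be made, but nothing in the conduct of the trial depends on it.

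**What to change.** Keep 9 per group and confirm which SD the 0.94 refers to. If it is the SD of the paired differences and testing is two-sided, replace the power sentence with:

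> Nine subjects per group give about 70% power (two-sided paired t-test, alpha 0.05, SD of the paired differences) for 0.94 SD and 80% power for 1.07 SD.

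If 0.94 is in SDs of single values, give the pre-post correlation from the preliminary data and recompute the power from it. If a one-sided test was intended for the directional mRNA hypothesis in subjects with obesity, prespecify it for that single test before analysis, and say that it replaces the ANOVA p-value there. State the alpha that applies to this outcome, so that it is clear whether 0.0125 is relevant.

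The cost is one or two sentences and, on the two-sided reading with the SD of the paired differences, a less favourable stated power. No extra enrolment or change of procedure is needed.
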